3.2 Statistical Analysis Issues

In the spirit of the ITT approach, data collected outside of a participant's visit window will be included in the analysis.

Due to the occurrence of a pandemic during the conduct of this study, there may be more than expected missing data. Any missing data will be tabulated as a separate category when reporting data summaries. If a substantial amount of endpoint data is missing (e.g., follow up data missing in at least 10% of participants), then secondary sensitivity analyses of the endpoints will be conducted using methods that relax the missing completely at random assumption to a missing at random assumption. For a univariate binary and quantitative outcome, respectively, a generalized linear model with a binomial or Normal error distribution will be used for estimation and testing. These secondary sensitivity analyses will include imputing the data under the most extreme scenarios of information missingness, such as assuming participants with missing data has an extreme value of the missing variable.

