5.1.2 Retention

Once a participant is enrolled into the study, the study site will make every effort to retain the participant in follow-up to minimize possible bias associated with loss-to-follow-up. An average retention rate of 95% will be targeted across sites.

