2.3 Randomization

Participants were randomized in a 3:1 ratio (VR:tablet) to the two arms of the study stratified by study site. The randomization scheme was generated and maintained by the MTN SDMC.

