2.5 Sample Size and Power

The target sample size was 200 mother-infant pairs randomized 3:1 to vaginal ring vs oral Truvada. A total of 197 mother-infant pairs were enrolled. The sample size is based upon feasibility, anticipated low drug concentrations, and the likelihood of a favorable safety profile. The statistical properties of the study are described using the probability of observed safety events defined in the primary endpoint. The probabilities of observing a safety event for various “true” event rates were calculated. For example, if the true safety event rate was 5%, the probability of observing zero safety events is 0.05% for the cohort size of 150 participants (DPV VR) and is 7.69% for cohort size of 50 participants (Truvada). An alternative way of describing the statistical properties is in terms of 95% confidence interval. For example, if none of the participants experience a safety event, the 95% exact 2-sided upper confidence bound for the true event rate is 2.43% for participant receiving the VR regimen and is 7.11% for participants receiving Truvada. The properties above also inform the hypotheses around drug detection where number of events is the number of participants with detectable drug levels. Further details of the statistical properties for this study are described in section 10.5 of the protocol.

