9. SECONDARY ENDPOINT ANALYSES

9.1 Adherence

For the secondary endpoint of adherence, all mothers will be included. A secondary sensitivity analysis will be conducted including only mothers with drug concentration results for at least one visit after Enrollment.

For women randomized to the VR arm, a combination of measures will be used to characterize use of study product. In addition to the summary of maternal plasma DPV concentrations as described above in section 8.3, the residual DPV levels in the returned used rings will be summarized by study visit.

For women randomized to Truvada, maternal FTC-TP and TFV-DP concentrations from DBS sample collections, as described above in section 8.3, will be used to quantify study product use.

Cut-point Analyses

Drug levels will be summarized (number and percent) by categories defined by the following cut-points for each product. Because DPV ring release rates have not been verified against directly observed use, the only comparable category for the two products is no use.

DPV ring:

No use (rate \leq 0.9mg/month)
Some release (0.9mg/month $<$ rate \leq 4.0mg/month)
High release (rate $>$ 4.0mg/month)

Truvada:

No use (<16.6fmol/punch)
Some use (16.6-699fmol/punch)
High use (\geq 700fmol/punch)

DPV release rate is defined as the amount of DPV released from the ring divided by the duration of time during which the participant had the ring. The amount of DPV release is calculated by subtracting the

amount of residual DPV in a returned ring from the amount of DPV in control rings from the same lot number.

The number and proportion of participants visits with concentrations indicative of non-adherence (no use) will be compared by study arm using generalized estimating equations (GEE) with a Poisson link, an offset of number of tests for drug concentration, an exchangeable correlation structure and robust errors. The comparisons will be done using the cut-point levels described above for the two study arms: 1) residual ring data for participants assigned to the VR arm and 2) plasma data for participants assigned to Truvada. Trends over time in study product use will be explored using GEE.

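### The missing-data plan names no model that would deliver its stated MAR analysis, makes the safety bounds conditional on the amount missing, and has an adherence sensitivity analysis that may repeat the main comparison

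*SAP*

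**What the plan says.** **Missing data (SAP 3.2).** The SAP expects more missing data than planned because of the pandemic. The response is conditional: "If a substantial amount of endpoint data is missing (e.g., follow up data missing in at least 10% of participants), then secondary sensitivity analyses" are to be run, using "methods that relax the missing completely at random assumption to a missing at random assumption". For a univariate binary or quantitative outcome, "a generalized linear model with a binomial or Normal error distribution will be used for estimation and testing". No covariates, weights, earlier-visit outcomes or imputation model are listed. The next sentence places imputation of extreme values within these same analyses. SAP 5 only refers back to 3.2. Protocol 10.8.4 has the same model sentence, and gives as its reason that missingness may depend on covariates or on the outcomes themselves.

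**Primary safety (SAP 3.1, 8.1, 8.2).** The set is everyone enrolled who received at least one dose. Results are percentages by arm with exact binomial intervals. No rule is given for a dosed participant whose safety follow-up is incomplete.

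**Adherence (SAP 3.1, 9.1).** All mothers are included. The arms are compared on no-use visits by a Poisson GEE with the number of drug concentration tests as offset. In addition: "A secondary sensitivity analysis will be conducted including only mothers with drug concentration results for at least one visit after Enrollment".

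**The concern.** There are three gaps between purpose and method.

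- A MAR analysis corrects something only if it conditions on variables that predict both missingness and outcome. None is named. If the model is fitted on arm alone, it is offered as a check but cannot differ from the result it checks.
- Extreme-value imputation is the analysis that would show how far early losses could move a rare-event rate. It rests on an MNAR assumption but is listed under MAR, and it is planned only when missingness is judged substantial. Adverse events are recorded when they occur, so a participant lost early leaves no empty field. Kept in the denominator, she or her infant counts as event-free, which is already the best case.
- A sensitivity analysis that drops mothers with no concentration result cannot change a model that such mothers never enter. Unreturned rings and missed dried blood spots (DBS) are absent from both fits.

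At stake is the upper confidence limit on serious and Grade 3 or higher events. SAP 2.5 uses that quantity to describe what the study can show.

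**Working it through.** **1. The plan's own figures (SAP 2.5; Protocol Tables 19 and 20).** P(0 events) at a true rate of 5% is 0.95^150 = 0.046% and 0.95^50 = 7.69%; the SAP gives 0.05% and 7.69%. The exact two-sided 95% upper limit with 0 events is 1 − 0.025^(1/n): 2.43% for n = 150 and 7.11% for n = 50. Both reproduce.

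**2. The named model on arm alone.** For binomial and Normal errors alike, the estimating equation in each arm is Σ(y − p) = 0 over observed participants, so p = events/observed. Inputs: "A total of 197 mother-infant pairs were enrolled", allocated 3:1. The split is not given; 197 × 3/4 = 147.75, so I assume 148 and 49. I also assume 7 and 2 observed events, with 14 and 5 participants missing. Both fitted models return 7/134 = 5.22% and 2/44 = 4.55%, exactly the complete-case proportions.

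**3. What conditioning would add.** Assume four equal sites with event rates of 2, 5, 10 and 20% and missingness of 2, 5, 10 and 40%.

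- True rate: (2 + 5 + 10 + 20)/4 = 9.25%.
- Complete case: (2×0.98 + 5×0.95 + 10×0.90 + 20×0.60)/(0.98 + 0.95 + 0.90 + 0.60) = 27.71/3.43 = 8.08%.
- Standardised over site: each site's rate is recovered from its observed members, and the equal-weight average is again 9.25%.

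A simulation of this setting gave 9.28, 8.08 and 9.25%.

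**4. Bounds for rare events.** The exact upper limit is the 0.975 quantile of Beta(x + 1, n − x). The worst case gives every unobserved participant an event. Counts of unobserved participants are assumed.

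| Arm | Observed events | Unobserved | Counted as event-free: upper limit | Worst case: rate, upper limit |
|---|---|---|---|---|
| Ring, n = 150 | 0 | 7 (4.7%) | 2.43% | 4.7%, 9.38% |
| Truvada, n = 50 | 0 | 4 (8.0%) | 7.11% | 8.0%, 19.23% |

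The last figure is also the entry for 4/50 in Protocol Table 20. With the non-zero counts of step 2, (14 + 5)/197 = 9.6% are missing, just under the example threshold:

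| Arm | Complete case (95% CI) | Worst case (95% CI) |
|---|---|---|
| Ring | 5.2% (2.1–10.5) | 21/148 = 14.2% (9.0–20.9) |
| Truvada | 4.5% (0.6–15.5) | 7/49 = 14.3% (5.9–27.2) |

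**5. Would the condition be met?** Protocol 5.1.2: "An average retention rate of 95% will be targeted across sites". SAP 6.2 counts retention visit by visit, and there are six follow-up visits (3 to 8). At 95% per visit, the share of participants missing at least one visit is 5% if the same people miss every visit, 1 − 0.95^6 = 26.5% if misses are independent, and 6 × 5% = 30% if different people miss each visit. Whether 10% is reached depends on how misses cluster and on what counts as missing. Retention alone does not settle it.

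**6. The adherence GEE.** The model is log E(no-use count) = log(tests) + β0 + β1·arm. With 0 tests, log(0) is undefined. In a fit to 60 simulated mothers, adding three with 0 tests made the fit fail. Giving those three an offset of log(1e-8) left the coefficients (−1.312, −0.135) and standard errors (0.378, 0.418) unchanged. So if the subset is defined by the same tests as the offset, the two GEE analyses are one analysis.

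**The case against.** Several points on the other side are sound.

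- **The SAP does not say the model is unadjusted.** It states a MAR aim, and SAP 5 speaks of adjusting for missingness; a model with suitable covariates could meet that aim. This stands. What can be shown is that the covariates are not specified.
- **A reader might infer that the bounds run only at 10% or more, and so never at 95% retention.** The documents do not support this. The 10% is an example, and step 5 shows it can be exceeded with the retention target met. The drawback is the reverse: whether to run the bounds is left to a judgement that can be made after seeing the data.
- **A reader might infer that nothing in the plan tests the effect of missing data.** SAP 3.2 does plan extreme-value imputation, and it tabulates missing data as a separate category without any condition. The remaining points are that the bounds are conditional and are grouped with analyses resting on a different assumption.
- **The worst case is severe.** The first ring or tablet is given at enrollment, and adverse events are collected from Week 1 and at early termination, so most people who leave will have been partly observed. The 2.43% and 7.11% are design illustrations with complete data. Both points stand: the results in step 4 are outer limits on assumed counts, not forecasts.
- **The adherence sets differ as written.** Self-reported outages, missed pills and reasons for non-use need no assay. If *results* means plasma in the ring arm, a mother may have a returned ring but no plasma result, or the reverse. This stands, so the point is confined to the GEE.
- **A missed DBS is a missed sample, not evidence of missed pills**, especially in a pandemic. Coding it as no use is therefore a bound only. Multiple imputation of rare events in about 50 Truvada mothers may also fail for sparse data.

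**Conclusion.** The point holds as a gap in specification, and it should be closed.

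1. The named model does not by itself deliver the MAR analysis the SAP describes. On arm alone it equals complete case; with covariates it could differ, but none is listed.
2. The extreme-value bounds are the right tool for primary safety, but they are classed under MAR and made conditional. Seven unobserved ring participants could raise the upper limit from 2.43% to 9.4%, and four on Truvada from 7.11% to 19.2%. These figures assume 0 observed events, no safety information on the unobserved participants, and an event in every one of them.
3. In the adherence GEE, the subset analysis repeats the main comparison, provided *drug concentration results* means the tests in the offset. This does not extend to the self-report summaries.

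It would be too strong to say that the plan has no sensitivity analysis for missing data, or that unreturned rings and missed DBS are known to reflect non-use; the documents support neither. The primary analyses are descriptive by arm, so no test result depends on this. What is affected is how much reassurance the upper limits can carry.

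**What to change.** 1. **Primary maternal and infant safety.** Define complete safety follow-up. Whatever the amount missing, report by arm the number without it, with best- and worst-case counts and exact 95% intervals, labelled as MNAR bounds.
2. **Any MAR analysis.** Condition on arm, site, and collected baseline or earlier-visit variables that predict missingness. Use a covariate-standardised GLM, or multiple imputation where event counts allow. List the variables in the SAP.
3. **Adherence GEE.** Replace the subset analysis with one that counts unreturned rings and missed DBS during prescribed use as no use. Present it as a bound beside the main result, not as the primary estimate. The inputs are already collected: SAP 6.4 tracks completion of DBS and used-ring procedures, SAP 6.5 records product not returned, and SAP 10.2 covers product holds.

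The cost is SAP wording and a few extra tables. The bounds will be wide and look less favourable than the complete-case intervals, so the text should say that they are limits and not estimates.

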4. INTERIM ANALYSIS AND DATA MONITORING COMMITTEE

No interim analysis was planned or performed for the MTN-043 study.

5. GENERAL ANALYSIS METHODS

Descriptive statistics will be used to assess group characteristics or differences by study arm. Categorical variables will be summarized using the number and percent in each category. The Pearson-Clopper method¹ will be used to obtain a 95% confidence interval (CI) on the proportion of binary variables where applicable. Continuous variables will be summarized using the number of non-missing values, mean, median, standard deviation, quartiles and range (minimum, maximum) unless otherwise indicated.

The study arms will be identified and formatted as "DPV vaginal ring" and "Truvada oral tablet".

When use of formal testing to assess differences is required, the following methods will be used unless otherwise specified: Fisher's exact test or logistical linear regression for categorical response variable; t-test or linear regression for continuous outcomes. Hypothesis tests for the primary and secondary endpoints comparing the two study arms will have a two-sided significance level of 5%.

Within study arm assessment of the change from baseline measurement to a follow up measurement will be analyzed using McNemar's test (for categorical response variables) or the paired t-test or Wilcoxon signed-rank test (for continuous variables).

To assess the adequacy of the randomization, participants in each of the two arms will be compared for baseline characteristics including demographics and laboratory measurements using descriptive statistics. No formal statistical comparisons will be performed.

As mentioned previously, there may be more than the usual amount of missing data in this study. Appropriate methods will be used to characterize and adjust for missingness as described in Section 3.2 above.

6. TRIAL PARTICIPANT DISPOSITION

6.1 Disposition of Participants

Enrollment of participants took place at four sites in Africa: Blantyre, Malawi; Zengeza Zimbabwe; Kampala, Uganda; Shandukani, South Africa (Johannesburg, SA). The mothers and infants screened and the reasons for those not enrolled will be summarized in tables by study site. The mother/infant pairs screened and enrolled by month will be summarized by study site. In addition, a consort diagram will describe the screening, eligibility, enrollment, randomization, and discontinuations from study participation. The consort diagram (or a separate table as appropriate) will describe the number of the participants with the minimum required data (from assays or eCRFs as described in Section 3.1 above) for inclusion in the primary and secondary analyses.

6.2 Retention

For each visit, a participant is expected to have returned to the site clinic within a protocol-specified visit window based on the enrollment visit date. The proportion of mothers and infants retained at a scheduled visit is obtained by dividing the number of participants who have completed the visit by the number of participants expected for that visit. Tables will be presented that show by visit the number and percentage of expected, retained, and missed visits in addition to mothers and infants lost-to-follow up or terminated early from the study by site and by arm. No formal statistical testing will be conducted.

6.3 Study and Study Product Discontinuation

The number and percentage of mothers and infants who completed the study, along with the number and percentages of participants who did not complete the study for reasons collected on the Study Termination eCRF will be presented in tables by site and by arm. Reasons for not completing the study include the following: death, unwilling or unable to comply with required study procedures, lost to follow up, investigator decision, refusal of further study product use, early study closure, protocol deviation, adverse event (mother and/or infant), withdrawal of consent by mother (or for the infant by the infant's mother), study terminated by sponsor, and other. No formal statistical testing will be conducted.

The number and percentage of mothers who completed the study product regimen, along with the number and percentages of mothers who did not complete the study product as specified per protocol for the reasons collected on the Discontinuation of Study Product eCRF will be presented in tables by site and by arm. Reasons for not completing the study product regimen per protocol include the following: death, refusal of further participation, unwilling or unable to comply with required study procedures, lost to follow up, investigator decision, refusal of further study product use, HIV infection, early study closure, protocol deviation, adverse event (mother or infant), withdrawal of consent by participant, study terminated by sponsor, acquisition of hepatitis B infection (for Truvada group only), allergic reaction to the study product, reported use of PrEP for HIV prevention outside of the study, reported use of PEP for potential HIV exposure, non-therapeutic infection drug use, pregnancy, and other. No formal statistical testing will be conducted.

6.4 Visit Adherence: Completion of Procedures

Completion of the following required and expected procedures for mothers will be evaluated: 1) social harms; 2) baseline behavioral assessment; 3) follow up behavioral assessment; 4) 3 month behavioral assessment; 5) in-depth interview (IDI); 6) baseline infant feeding assessment; 7) follow up infant feeding assessment; 8) use of vaginal products; 9) physical exam; 10) pelvic exam; 11) pregnancy test; 12) HIV-1 test; 13) hepatitis B surface antigen test; 14) blood serum chemistry; 15) hematology; 16) syphilis serology; 17) NAAT (pelvic) for GC/CT/TV; 18) plasma for archive; 19) dried blood spot (DBS) for TFV-DP and FTC-TP drug levels (for Truvada group only); 20) plasma for DPV drug levels (DPV VR group only); 21) breastmilk for drug levels; 22) vaginal swab for microbiota; 23) vaginal gram stain; 24) vaginal swab for biomarkers; 25) used vaginal ring (DPV VR group only).

Completion of the following required and expected procedures for infants will be evaluated: 1) physical exam; 2) infant ages and stages assessment; 3) DBS for TFV-DP and FTC-TP drug levels (for infants of mothers in Truvada group only); 4) plasma for DPV drug levels (for infants of mothers in DPV VR group only).

Tables displaying the number and percentages of participant-visits in which these procedures were completed, by arm and by site, will be presented. No formal statistical testing will be conducted.

6.5 Protocol Deviations

Protocol deviations, as collected in the Protocol Deviations Log eCRF, will be reported. The number and percentage of participants with protocol deviations, along with the number and percentage of participants experiencing each type of protocol deviation, will be tabulated by site and by arm. Type of deviations include: inappropriate enrollment, failure to follow randomization or blinding procedures, study product management deviation, study product dispensing error, study product use/non-use deviation, study product sharing, study product not returned, conduct of non-protocol procedure, improper AE/EAE follow up, unreported AE or EAE, breach of confidentiality, physical assessment deviation, lab assessment deviation, mishandled lab specimen, staff performing duties that they are not qualified to perform, questionnaire administration deviation, counseling deviation, use of non-IRB/EC-approved materials, use of excluded concomitant medications, devices, or non-study products, informed consent process deviation, visit completed outside of window, and other.

Additionally, a listing with all the reported protocol deviations will be presented. The listing will include the type of deviation, the deviation date, the date that the site was aware of the deviation, whether the deviation was reported to the local IRB/EC, whether the deviation was reported to DAIDS, the description of the deviation, the steps taken to address the deviation, and the steps taken to prevent future occurrences. No formal statistical testing will be conducted.

7. BASELINE DATA

Baseline characteristics of all enrolled participants will be compared by their study product assignment as randomized and by site. No formal statistical comparisons will be performed for any of the baseline results described below.

7.1 Demographics

Baseline demographic characteristics will include ethnic group or tribe, age and age category, sex at birth (for infants), number of sex partners in participant's lifetime (for mothers), and whether the participant has a primary sex partner (for mothers). Tables for mothers and infants will include summary statistics appropriate for the measurement scale by site and by arm.

